	
System in a post-market (commercial device use) setting will be enrolled and will be followed for 24 months post index procedure.
 
Enrolled subjects will undergo endovascular PAD treatment that includes atherectomy using the AURYON system, according to institutional standard of care. Data collection will include prospective data collection and medical record review of procedures performed according to standard of care, at the study protocol specific follow up time-points.

OBJECTIVES:	To evaluate the safety and efficacy of AURYON Atherectomy System in the treatment of de novo, re-stenotic and ISR lesions in infra-inguinal arteries of Peripheral Artery Diseases (PAD) subjects, in a real-world setting. This is a pilot registry study towards a subsequent large pivotal registry (PATHFINDER II).
ENDPOINTS:	
Primary Endpoints:
 
 1. Primary Efficacy: Acute Procedural Success Percentage of subjects with successful revascularization of target vessel defined as $\leq 30\%$ residual stenosis at the index lesion post atherectomy using the AURYON system and final adjunctive treatment (if required), as evaluated by angiographic corelab. 2. Primary Safety: Percentage of subjects with freedom from peri-procedural major adverse events (PPMAE), defined as (a) flow-limiting dissection, (b) clinically significant distal embolization, (c) bailout stenting, (d) major/unplanned amputation, (e) target vessel perforation requiring endovascular or surgical repair or (f) death, till discharge. 
Secondary endpoint(s):
 
 1. Rate of device related complications requiring intervention, defined as peri procedural MAEs, reported by the operating physician as caused directly due to the use of the AURYON device. 2. Rates of post-discharge MAEs over time; defined as: (a) Unplanned target limb amputation, (b) cardiovascular death, (c) clinically driven target lesion revascularization¹, (d) target vessel revascularization (TVR). 3. Patency rate, defined as (1) $< 50\%$ stenosis at the treated lesion, with peak systolic velocity ratio (PSVR) of < 2.5, as

[figure not shown]
¹ Clinically-Driven Target Lesion Revascularization (CD-TLR), defined as a reintervention performed for $\geq 50\%$ diameter stenosis (confirmed by angiography) within 5 mm of the target lesion after documentation of recurrent clinical symptoms of PAD following the index procedure.

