	
assessed quantitatively by Duplex ultrasonography (DUS); OR, (2) for BTK lesions: freedom from occlusion (100% stenosis by DUS) combined with freedom from CD-TLR, at 6, 12, and 24 months.
 
4. Clinical outcomes, defined as change in ankle brachial index (ABI or TBI if needed), walking impairment questionnaire (WIQ), and Rutherford category at 6, 12, and 24, months, compared to baseline
 
Exploratory endpoint(s):
 
1. Intravascular ultrasound assessment pre- and post-Auryon and correlation with angiographic findings (e.g. lesion length, MLA -minimal lumen area gain, calcium severity and removal, etc.). This endpoint will be analyzed only for cases that used IVUS as a routine practice in the index procedure.

STUDY POPULATION:	
Patients with infra-inguinal PAD undergoing atherectomy with the AURYON Atherectomy System.
 
Inclusion Criteria A potential subject will be included in the study if he/she meets all the following inclusion criteria:
 
 1. Subject is ≥ 18 years old. 2. Subject is a candidate for atherectomy for infra-inguinal peripheral artery disease. 3. Documented symptomatic atherosclerotic peripheral artery disease with claudication or critical limb ischemia (CLI) (Rutherford Classification 2-5). 4. Subject is capable and willing to comply with the scheduled follow up 5. Subject is able and willing to sign a written Informed Consent Form (ICF). 
Exclusion Criteria A potential subject will be excluded from the study if he/she meets any of the following exclusion criteria:
 
 1. Target lesion is in an arterial bypass. 2. Planned use of another atherectomy device in the same procedure 3. Co-morbid condition(s) with less than 1yr anticipated survival that could limit the subject's ability to participate in the trial or to comply with follow-up requirements or impact the scientific integrity of the study.

	4. Participating in another study on an interventional non-cleared device, that could impact the study results

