DESCRIPTION OF SITES/FACILITIES ENROLLING PARTICIPANTS:	
This study will be conducted at sites where eligible PAD patients are routinely treated with atherectomy by AURYON Atherectomy System.
 
Total enrollment of approximately 100 subjects at approximately 10 sites in the US.
 
To reduce bias by sites, each site may enroll up to 15 eligible subjects whom have successfully completed their index atherectomy treatment with the AURYON system and with analyzable imaging for the primary efficacy analysis.

DESCRIPTION OF STUDY PROCEDURE:	Atherectomy by the AURYON system, of infra-inguinal stenoses, occlusions or in-stent restenosis (ISR).
STUDY DURATION:	The study duration is expected to be two and a half (2.5) years: 6 months to enroll and two (2) years to follow up all subjects.
PARTICIPANT DURATION:	Two (2) years
PRIMARY ANALYSIS PLAN:	
As this is a pilot registry study, no formal hypotheses are defined; rather statistical analyses will be descriptive in nature and will serve to provide estimates of the primary and secondary study endpoints.
 
Also, no formal sample size calculation was performed. The number of enrolled subjects will allow for sufficient safety monitoring and evaluation of the safety and efficacy endpoints and will provide point estimates for the large-scale registry.
 
Analysis sets:
 
Intent-to-treat (ITT) population: The intent-to-treat (ITT) population will consist of all subjects who signed the informed consent form and underwent procedure with an attempt of using the AURYON system.
 
Modified Intent-to-treat (mITT) population: The modified Intent-to-treat (mITT) population will consist of all ITT subjects who underwent atherectomy using the AURYON system for at least one lesion.
 
Per-protocol (PP) population

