	
The per-protocol (PP) population will consist of all mITT subjects for whom the AURYON catheter fully crossed at least one target lesion.
 
If a subject does not undergo complete procedure, either due to early or intraoperative non-eligibility of inclusion/exclusion criteria or due to missing evidence of significant arterial disease ($\geq 50\%$) by fluoroscopy angiogram in the index procedure, the subject will be considered as a screen failure. Screen failures will not be included into ITT population and will not be followed or part of the analysis.
 
If a subject undergoes an atherectomy attempt but the AURYON system could not be successfully used in any target lesion, the subject will be included into ITT population but excluded from mITT and PP populations. That subject will not be followed-up after discharge.
 
If a subject undergoes atherectomy using the AURYON system but the AURYON catheter cannot fully cross the target lesion, the subject will be included into ITT and mITT populations but excluded from PP population. That subject will be followed-up after discharge at 30-day, 6-month, 12-month and 24-month visits.
 
Analyses of all primary & secondary endpoints will be conducted in both the mITT and PP populations. The ITT population will serve as the primary set for safety assessments.

RATIONALE FOR NUMBER OF PATIENTS:	
With a total of 100 patients successfully treated by AURYON system in this study cohort, this study will serve as an unpowered pilot registry, towards a larger powered registry study that is planned to include approximately 1000 patients.

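### A target lesion finished with an unplanned second atherectomy device can be scored as an AURYON procedural success, and the plan neither separates nor counts such cases

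*Combined protocol and SAP*

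**What the plan says.** All references are to the combined protocol and SAP, Section 2 (Protocol Summary), unless stated.

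- **Exclusion criterion 2** removes subjects with "Planned use of another atherectomy device in the same procedure". Unplanned use is not mentioned there or elsewhere in the text available, which ends with the schedule of activities in Section 4.
- **Primary efficacy** (Endpoints) requires no more than 30% "residual stenosis at the index lesion post atherectomy using the AURYON system and final adjunctive treatment (if required), as evaluated by angiographic corelab". Adjunctive treatment is not defined.
- **Primary safety** (Endpoints) is freedom from six peri-procedural events. The first four are "a) flow-limiting dissection, (b) clinically significant distal embolization, (c) bailout stenting, (d) major/unplanned amputation"; the other two are a perforation that needs repair, and death before the subject leaves hospital. Bailout stenting is on the list; a change to another atherectomy device is not.
- **Secondary endpoint 1** counts those same events when "reported by the operating physician as caused directly due to the use of the AURYON device".
- **Analysis sets** (Primary Analysis Plan): mITT is "all ITT subjects who underwent atherectomy using the AURYON system for at least one lesion". PP further requires that the catheter fully crossed at least one target lesion. Subjects in whom AURYON could not be used successfully in any target lesion stay in ITT only. "If a subject undergoes atherectomy using the AURYON system but the AURYON catheter cannot fully cross the target lesion", the subject stays in mITT but leaves PP. Primary and secondary endpoints are analysed in mITT and PP; ITT is the main set for safety.
- **Table 1** (Section 4) records peri-procedural events and other procedural complications, with no separate item for other devices used.

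**The concern.** The registry sets out to evaluate the safety and efficacy of AURYON, and its declared product is a set of point estimates for a later registry of about 1000 patients. An operator who starts with AURYON and finishes the same lesion with another atherectomy device has found AURYON insufficient for that lesion, at least in part. If the core laboratory then reads 30% or less, the definition as written lets that result enter the numerator. The exclusion criterion does not act, because it looks only at what was planned, and no endpoint or listing shows how often this happened.

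At stake is a success rate that may be too high by an amount no reader could recover from the planned outputs. Later patency and CD-TLR in those lesions would also reflect the combined effect of AURYON, the second device and any other adjunct.

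**Working it through.** The plan has no sample size or power figure to reproduce: it is descriptive and states no hypothesis. The check is to trace an unplanned switch through the rules, then show the arithmetic under stated assumptions.

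**Step 1. Which switches can be scored as a success?**

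| What happened with AURYON before the switch | mITT | PP | Can the final result count as efficacy success? |
|---|---|---|---|
| Could not be used in any target lesion | No | No | No; the subject is in neither efficacy set |
| Used, but did not cross | Yes | No | Yes, in mITT only |
| Crossed at least one target lesion | Yes | Yes | Yes, in both |

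The second and third rows depend on reading the second device as adjunctive treatment, which the wording permits but does not state. A separate route is the screen-failure rule: a subject whose procedure is incomplete because of intraoperative non-eligibility leaves all analysis sets. That rule does not reach a completed procedure in which a switch was not planned.

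**Step 2. Does primary safety capture the switch?** The switch itself matches none of items (a) to (f). A listed event that occurs during or after it, up to discharge, does count, because the primary definition does not require attribution to AURYON.

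**Step 3. Size.** Inputs: N = 100, the approximate planned enrolment, taken here as the size of the analysis set. S, the number scored as successes, and k, the number of those reached after a switch, are assumptions; the documents give neither.

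- Rate as the definition permits: S/N.
- Rate with switched successes scored as failures: (S − k)/N.
- Difference: k/N, so 1/100 = 1 percentage point per switched success.
- A switched subject left above 30% is already a failure and adds nothing to k.

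With exact (Clopper-Pearson) 95% intervals:

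| S | k | Rate | 95% CI |
|---|---|---|---|
| 95 | 0 | 95% | 88.7 to 98.4% |
| 95 | 2 | 93% | 86.1 to 97.1% |
| 95 | 5 | 90% | 82.4 to 95.1% |
| 95 | 10 | 85% | 76.5 to 91.4% |
| 90 | 5 | 85% | 76.5 to 91.4% |
| 98 | 5 | 93% | 86.1 to 97.1% |

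**Step 4. Relevance to the later registry.** At n = 1000 and an assumed 95%, the approximate 95% half-width is 1.96 × √(0.95 × 0.05/1000) = 1.96 × 0.0069 = 0.0135, or about 1.4 points. If the same definition were carried forward, a switched-success share of 2% or more would shift the estimate by more than its sampling error.

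**The case against.** The strongest reply is that the endpoint is procedural by name and by construction. It is read after adjunctive treatment, in a real-world setting under institutional standard of care, and does not claim to measure AURYON alone. Scoring every switch as a failure whatever the final stenosis turns it into something closer to a device-success endpoint. It would also treat another atherectomy device more severely for efficacy than a bailout stent, which is a safety event but not an efficacy failure. This stands as an argument against making automatic failure the only acceptable scoring. It does not answer the need to define the adjunct and count the switches: accepting adjuncts in general does not settle whether a device of the same class as the one under study is one of them.

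A reader might also infer more than the documents support:

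- *That the plan counts every switch as an AURYON success.* No such rule is stated. The wording permits it, and the analysis sets remove subjects in whom AURYON could not be used in any target lesion, and remove non-crossers from PP. What counts as successful use is undefined, so some cases of poor debulking might leave mITT as well.
- *That a switch escapes the safety endpoint altogether.* Only the switch itself does. Listed complications after it count, and a switch is not in itself a harm.
- *That exclusion 2 shows the sponsor regards a second device as a confounder.* No rationale for the criterion is given.
- *That a bias of a particular size is present.* The range starts at zero.

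A definition of adjunctive treatment, or a form item for other devices, may appear after Section 4; that cannot be ruled out.

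**Conclusion.** The point holds in a limited form. As written, exclusion 2 and the primary efficacy definition together allow a result obtained with an unplanned second atherectomy device to be scored as acute procedural success, in mITT for subjects in whom AURYON was used and in both mITT and PP where it crossed at least one target lesion. The bias in the estimate of AURYON efficacy, where there is any, is upward. That direction follows from taking AURYON without another atherectomy device as the quantity of interest.

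The size is unknown: zero if no switch ends at 30% or less, and otherwise 1 point per such subject at n = 100. The figures above illustrate assumed success and switch counts and predict nothing. The absence of formal hypotheses does not remove the point, because the estimate is what the pilot is meant to deliver. It is a cheap improvement, not a flaw that undermines the study.

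**What to change.** 1. State in the primary efficacy definition that adjunctive treatment does not include another atherectomy device.
2. Record on the procedure form any unplanned use of another atherectomy device in the target lesion, and report the number of subjects by analysis set.
3. Report acute procedural success with these subjects scored as failures. At minimum, make this a pre-specified sensitivity analysis shown beside the rate based on the final angiographic result.
4. Report patency and CD-TLR with and without these lesions.

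This changes scoring and reporting only and leaves the operator's choice of treatment as it is. The cost is a sentence in the endpoint definition, one form item, a few extra table rows and a success rate that may be slightly lower.

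### The per-site cap and the stated 100 are counted on post-procedure success, in conflict with the any-attempt ITT set, and failed device attempts are absent from the efficacy denominator

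*Combined protocol and SAP*

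**What the plan says.** All of the relevant text is in section 2, Protocol Summary, of the combined protocol and SAP.

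- **Description of sites, total:** "Total enrollment of approximately 100 subjects at approximately 10 sites in the US". No success or imaging condition is attached.
- **Description of sites, cap:** "each site may enroll up to 15 eligible subjects whom have successfully completed their index atherectomy treatment with the AURYON system", continuing "and with analyzable imaging for the primary efficacy analysis". The stated aim is to limit bias by site.
- **Rationale for number of patients:** "With a total of 100 patients successfully treated by AURYON system in this study cohort". Imaging is not mentioned.
- **Primary analysis plan, ITT:** "all subjects who signed the informed consent form and underwent procedure with an attempt of using the AURYON system".
- **Primary analysis plan, failed attempts:** if the device could not be used successfully in any target lesion, "the subject will be included into ITT population but excluded from mITT and PP populations". Also, "That subject will not be followed-up after discharge".
- **Primary analysis plan, use of the sets:** primary and secondary endpoints are analysed in mITT and PP. ITT is the main set for safety.
- **Primary analysis plan, size:** "no formal sample size calculation was performed".

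The study description has enrolled subjects going on to treatment, and Table 1 in section 4 places consent before the procedure. Neither successful completion nor successful treatment is defined, and no replacement rule is stated.

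**The concern.** Three counting units are in use: subjects enrolled, subjects attempted and subjects treated successfully. The last is known only after the procedure, and so is whether the imaging is analyzable. If sites work to the cap sentence as written, they need not count a failed or unreadable case as enrolled, and they can go on recruiting until enough countable cases have accrued.

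The study's product is a set of point estimates for a larger registry of about 1000 patients. A success rate computed on a denominator without the failed attempts would be carried forward as if it described all patients in whom the device was tried. Attempts that were never logged are also hard to recover later.

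**Working it through.** **1. The plan's own figure.** The 100 cannot be reproduced, because the plan gives no precision target, rate or dropout behind it. The only check available is capacity: 10 sites × 15 = 150 places, against a mean of 100/10 = 10 per site. At the cap, 100/15 = 6.7, so at least 7 sites would be needed. The cap and the total are compatible in number. The conflict is in what is counted.

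**2. The counting units side by side.**

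| Statement | Unit counted | Known before the procedure? |
|---|---|---|
| Total enrolment, about 100 | Enrolled subjects | Yes |
| Site cap, 15 | Success and analyzable imaging | No |
| Rationale, 100 | Success | No |
| ITT set | Consent plus attempt | Known once the attempt begins, whatever its result |

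The two success-based counts cannot both equal the enrolment or ITT count unless no attempt fails.

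**3. Attempts needed (illustration).** Let f be the share of attempts that do not count. The documents give no value, so f is assumed. For the 100, f covers unsuccessful attempts. For the cap it also covers unreadable imaging.

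Attempts for 100 countable subjects = 100/(1 − f), rounded up. Attempts permitted by one site's cap = 15/(1 − f).

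| f | Attempts for 100 | Attempts under a cap of 15 |
|---|---|---|
| 5% | 100/0.95 → 106 | 15.8 |
| 10% | 100/0.90 → 112 | 16.7 |
| 20% | 100/0.80 → 125 | 18.8 |

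**4. Does recruiting on to 100 successes bias the rate by itself?** Hardly, if every attempt stays in the denominator. Stopping at r successes biases the observed proportion upward by roughly p(1 − p)/r. With r = 100:

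- p = 0.90: 0.90 × 0.10/100 = 0.0009, about 0.1 percentage points
- p = 0.80: 0.80 × 0.20/100 = 0.0016, about 0.16 percentage points

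**5. What happens if uncounted attempts leave the denominator?** Suppose that 95 of 100 countable subjects meet the efficacy endpoint, and that every uncounted attempt is scored as not successful. The 95 is also assumed. Intervals are Clopper-Pearson 95%.

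| f | Success over all attempts | Gap from 95/100 = 95.0% (88.7 to 98.4) |
|---|---|---|
| 5% | 95/106 = 89.6% (82.2 to 94.7) | 5.4 points |
| 10% | 95/112 = 84.8% (76.8 to 90.9) | 10.2 points |
| 20% | 95/125 = 76.0% | 19.0 points |

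At f = 10% the all-attempts rate already lies below the interval reported on the countable subjects. The gap is an upper bound for each f, since some subjects with unreadable imaging will have had a good result.

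**6. Which rule removes the failed attempts?** Under the plan as written it is mainly the choice of analysis sets. A failed device attempt is kept in ITT but excluded from mITT and PP, and no ITT analysis of efficacy is stated. Rewording the cap and the target alone would therefore leave the efficacy denominator unchanged.

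**The case against.** The strongest reply is that this is loose wording in an unpowered, descriptive pilot, and that other text settles it. Consent precedes the procedure, enrolled subjects go on to treatment, and failed attempts are explicitly kept in ITT and analysed for safety. Much of that stands, and it rules out several stronger readings that a reader might infer:

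- **That failures vanish from the study.** The ITT rules say otherwise. What the documents leave open is whether a site following the cap sentence would log every such case.
- **That the 100 requires analyzable imaging.** The imaging condition is attached to the site cap only. Neither statement of the 100 contains it.
- **That enrolment selects on the primary outcome.** Primary efficacy is core-lab residual stenosis of at most 30%. Success of device treatment is undefined and is not shown to be the same thing. The mITT set keeps treated subjects whose lesion was not fully crossed, and its definition removes nobody for residual stenosis above 30%.
- **That failures are replaced by rule.** No such rule is written. Replacement is only implied by counting successes.
- **That the cap defeats its purpose.** It still limits each site to 15 countable subjects. The illustration adds about 1 to 4 attempted subjects per site, and the planned mean of 10 is below the cap.

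It is also fair to object that scoring unreadable imaging as failure is a choice, and that the documents do not show which way such losses bias the rate. What the reply does not answer is the conflict between the counts, or the lack of any efficacy estimate that includes failed attempts.

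**Conclusion.** The point holds in limited form. Two statements that govern study size and site contribution depend on post-procedure results, and they disagree with the plain enrolment total and with the ITT definition. Independently of that, acute procedural success is planned only on sets that exclude failed device attempts.

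The direction for failed attempts is predictable: excluding them can only raise the success rate. The size is not known. The illustrative gaps of 5.4 to 19.0 points rest on an assumed 5% to 20% of uncounted attempts, an assumed 95% success rate among the rest, and the scoring of every uncounted attempt as not successful. Continued recruitment alone accounts for only 0.1 to 0.2 points.

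With no hypothesis test, there is no effect on type I error or power. The risk is an optimistic estimate passed to the larger registry. This should be fixed, but it does not undermine the study.

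**What to change.** 1. Define enrolment as ITT entry: consent given and an AURYON attempt begun.
2. Apply both the total of about 100 and the cap of 15 per site to consecutive eligible subjects on that count, and state that failed attempts and unreadable imaging are not replaced.
3. Restate the rationale as about 100 attempted. Define successful treatment, or drop it from the counting rules.
4. Report acute procedural success in ITT alongside mITT and PP, with failed device attempts counted as not successful. The endpoint is assessed at the procedure, so this needs no extra follow-up visits.
5. Handle unreadable imaging in sensitivity analyses: once counted as failure, and once using the site-read stenosis if available.

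The cost is protocol and SAP wording, slightly fewer than 100 subjects in mITT and PP, and a somewhat lower reported success rate. The counting rules should be settled before or during enrolment, because attempts that were not logged cannot be reliably reconstructed.

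### The per-protocol set has no eligibility condition, and the screen-failure rule treats the same breach differently depending on whether it was recognised in time to stop the procedure

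*Combined protocol and SAP*

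**What the plan says.** All the relevant text is in the combined protocol and SAP, section 2 (Protocol Summary), under Primary Analysis Plan. The three sets are nested:

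- **ITT:** "all subjects who signed the informed consent form and underwent procedure with an attempt of using the AURYON system".
- **mITT:** the set "will consist of all ITT subjects who underwent atherectomy using the AURYON system for at least one lesion".
- **PP:** "The per-protocol (PP) population will consist of all mITT subjects for whom the AURYON catheter fully crossed at least one target lesion".

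The screen-failure paragraph that follows opens: "If a subject does not undergo complete procedure, either due to early or intraoperative non-eligibility of inclusion/exclusion criteria". It gives one alternative ground, that the index angiogram shows no stenosis of 50% or more. The consequence is: "Screen failures will not be included into ITT population and will not be followed or part of the analysis".

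Two further paragraphs deal with procedures that fall short for other reasons. Where an attempt is made but the device cannot be used in any target lesion, "the subject will be included into ITT population but excluded from mITT and PP populations". Where atherectomy is done but the catheter cannot fully cross, the subject stays in ITT and mITT and leaves PP only.

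On use of the sets: "Analyses of all primary & secondary endpoints will be conducted in both the mITT and PP populations". ITT is named as the main set for safety.

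**The concern.** A per-protocol set is normally read as the subjects who met the entry criteria and were treated as planned. It is usually reported beside a broader set to show whether protocol breaches move the result. Here the set with that name applies a technical test, crossing, and no eligibility test. Take a subject who breaches exclusion criterion 1 ("Target lesion is in an arterial bypass"). If that subject is treated and the lesion is crossed, the subject counts as per-protocol.

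The only place where eligibility affects the sets is the screen-failure rule, and that rule depends on an intraoperative event: whether the procedure was left incomplete because of the breach. Two subjects with the same breach can therefore be handled in opposite ways.

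All primary and secondary endpoints are estimated in PP as well as mITT, and the pilot is meant to supply point estimates for a registry of about 1000 patients. In a descriptive study, the population to which an estimate refers is most of what the estimate means. A second issue concerns safety. The screen-failure rule can remove from ITT a subject in whom the device was already attempted, and the primary safety endpoint counts events from the procedure to discharge.

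**Working it through.** The plan states no figure on this point, so the check is on the text. Take one fixed eligibility breach and follow it through the rules of section 2.

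| Case, same breach in each | ITT | mITT | PP | Rule that decides |
|---|---|---|---|---|
| A. Recognised before any device attempt; procedure not completed for that reason | out | out | out | Screen failure; agrees with the ITT definition, as there was no attempt |
| B. Recognised after a device attempt; procedure not completed for that reason | **in** by the ITT definition, **out** by the screen-failure rule | in or out, following ITT, if atherectomy was done in a lesion | in or out, following mITT, if a lesion was crossed | Two rules in conflict |
| C. Not recognised; procedure completed, lesion crossed | in | in | in | Set definitions only |
| D. Not recognised; atherectomy done, not crossed | in | in | out | Non-crossing, not the breach |
| E. Not recognised; device attempted, could not be used | in | out | out | Device-not-usable paragraph |

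Four results follow.

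1. In no case does PP remove a subject because of the breach itself. Case C shows that PP retains it, and in case D the removal is for non-crossing. Comparing PP with mITT isolates crossing and says nothing about eligibility.
2. A and C carry the same breach and end at opposite extremes. They differ in whether the breach was recognised in time to stop.
3. D and E show that falling short procedurally does not make a subject a screen failure. The non-completion must be caused by ineligibility or by absent disease.
4. B cannot be resolved from the text. The subject meets every element of the ITT definition, yet the screen-failure paragraph takes the subject out of ITT and out of all analysis.

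**Possible size (illustration only).** The documents give neither a success rate nor a violation rate. Assume 90 successes among 100 PP subjects: 90.0%, exact (Clopper-Pearson) 95% CI 82.4% to 95.1%. Assume k of the 100 are ineligible and are removed. The extremes are (90 − k)/(100 − k) if all k were successes and 90/(100 − k) if all k were failures:

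- k = 2: 88/98 = 89.8% to 90/98 = 91.8%
- k = 5: 85/95 = 89.5% to 90/95 = 94.7%
- k = 10: 80/90 = 88.9% to 90/90 = 100%

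In the other direction, assume m stopped ineligible subjects were added back and all counted as non-successes. The rate is 90/(100 + m): 88.2% for m = 2, 85.7% for m = 5 and 81.8% for m = 10. These are outer bounds under assumed counts. They show that the estimate could move either way, not that it will move by any given amount.

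**The case against.** **Eligibility is a condition of entry.** The study description enrols eligible subjects, and the inclusion criteria must all be met. The schedule of activities (section 4) places Rutherford category and angiographic evaluation of the target lesion before the procedure, and planned use of another atherectomy device is known in advance. Breaches that survive to a completed procedure should therefore be enrolment errors, and nothing in the documents suggests they are common. This stands as an argument about frequency. It does not say how such a subject is analysed once found. The reference to eligible subjects in the description of sites limits enrolment per site and is not an analysis-set rule.

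**PP is openly defined as a crossing set.** The definition is clear, mITT is reported beside it, and no hypothesis is tested. This limits the importance of the point and makes renaming the set an acceptable remedy for the PP part. It does not settle the conflict with ITT.

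**A stronger reading.** A reader might infer that ineligible subjects are kept or dropped according to how well their procedure went, so that the sets select on outcome. The documents do not support this. Removal requires that ineligibility, or absent disease, be the reason for non-completion; ineligible subjects whose procedure fell short for another reason stay in ITT (cases D and E). A reader might also infer that PP success is biased in a known direction. That would need both a violation rate and a success rate in ineligible subjects, and neither is given. Some exclusions, such as limited life expectancy or participation in another device study, have no evident link to residual stenosis.

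**The text is partial.** Only the compliance statement, the summary and the schedule were available. A later section could define PP further or cover deviations, and that could not be checked.

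**Conclusion.** The point holds on the text available. No analysis set requires the entry criteria to be met beyond consent. PP adds only crossing, and the single rule that acts on ineligibility depends on whether the breach was recognised and the procedure stopped for it. PP therefore cannot serve as a check on mITT for eligibility breaches. Separately, the screen-failure paragraph and the ITT definition contradict each other for a subject found ineligible after a device attempt, and this affects the primary safety set.

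The size and direction of any numerical effect are unknown. The importance is low: the study is descriptive and unpowered, mITT is reported alongside, and pre-procedure checks should keep breaches few. The point is nevertheless worth correcting before analysis because these estimates are meant to inform the larger registry. The conclusion assumes that no later section supplies an eligibility condition for PP or a different rule for ineligibility found during the procedure.

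**What to change.** 1. **PP definition.** Define PP as mITT subjects who met every inclusion criterion and no exclusion criterion, and in whom the catheter fully crossed at least one target lesion. Apply the eligibility condition regardless of when the breach was found. List the subjects removed for it, by criterion. If the sponsor prefers a pure crossing set, give it a name that says so and do not present it as per-protocol.
2. **ITT and screen failure.** Reconcile the screen-failure paragraph with the ITT definition, so that a subject in whom the device was attempted stays in ITT for safety whenever the ineligibility was found. Screen failure then covers only subjects with no device attempt. State in the same paragraph whether such a subject enters mITT when atherectomy was performed, and what data are collected for that subject.

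With both changes, cases B to E are treated alike with respect to the breach: in ITT, out of PP, and in or out of mITT only by whether atherectomy was done. Adding the PP condition alone would leave the ITT conflict in place, because screen failures would still be removed from ITT.

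The cost is one sentence in the PP definition, a revised screen-failure paragraph and one listing. PP becomes slightly smaller.
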